6.6.14. Surveillance for RSV-RTI and wheezing

Surveillance period for RSV-RTI and wheezing will start at Visit 1 (after Dose 1) until the final visit (Visit 11 [Day 730]). In order to timely detect RSV-RTI and to ensure cases are timely captured by the study sites, both active and passive surveillance will be conducted as described in Section 9.2. Contacts for active and passive surveillance will be recorded in the eCRF.

If an assessment visit is performed (refer to Section 9.2.4), this visit will be recorded in the eCRF, as well as signs and symptoms. Signs and symptoms to be recorded in the eCRF are listed in the SPM.

At the first vaccination visit (Visit 1 [Day 0]), RTI episode cards will be provided to the subject's parent(s)/LAR(s). At subsequent study visits, new RTI episode card(s) will be distributed as needed. The subject's parent(s)/LAR(s) will record the start date and the end date of the following symptoms: cough, runny nose, blocked nose, difficulty in breathing, or wheezing. The subject's parent(s)/LAR(s) will be instructed to return the completed RTI episode card to the investigator at the next visit or by mail (e-mail or postal mail). The investigator will transcribe the collected information into the eCRF. Any unreturned RTI episode card will be sought from the subject's parent(s)/LAR(s) through telephone call(s) or any other convenient procedure.

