10.2.1. Subject withdrawal from the study

From an analysis perspective, a 'withdrawal' from the study refers to any subject who did not come back for the concluding visit foreseen in the protocol.

All data collected until the date of withdrawal/last contact of the subject will be used for the analysis.

A subject is considered a 'withdrawal' from the study when no study procedure has occurred, no follow-up has been performed and no further information has been collected for this subject from the date of withdrawal/last contact.

Investigators will make an attempt (e.g. three telephone calls and a certified letter to the last known address) to contact those subjects who do not return for scheduled visits or follow-up.

Information relative to the withdrawal will be documented in the eCRF. The investigator will document whether the decision to withdraw a subject from the study was made by the subject's parent(s)/LAR(s), or by the investigator, as well as which of the following possible reasons was responsible for withdrawal:

- SAE.
- Non-SAE.
- Protocol violation (specify).
- Consent withdrawal, not due to an AE*.
- Moved from the study area.
- Lost to follow-up.
- Other (specify).

*In case a subject is withdrawn from the study because the subject's parent(s)/LAR(s) has withdrawn consent, the investigator will document the reason for withdrawal of consent, if specified by the subject's parent(s)/LAR(s), in the eCRF.

Subjects who are withdrawn from the study because of SAEs/AEs must be clearly distinguished from subjects who are withdrawn for other reasons. Investigators will follow subjects who are withdrawn from the study as result of a SAE/AE until resolution of the event (see Section 9.5.2).

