11.10. Analysis of RTI and LRTI

The analysis will be performed on the TVC on two pooled groups (i.e. pooled RSV and pooled Placebo) separately for first and second RSV seasons and overall.

The proportion of subjects with at least one RSV-associated RTI (with 95 % CI) will be calculated. The same descriptive analysis will be performed for subjects with at least one RSV-associated LRTI and those with at least one RSV-associated severe LRTI.

As primary analysis, the assessment of RSV infection will be performed using the quantitative RT-PCR according to standardized case definitions (see [Table 4](#)) based on the available WHO case definitions.

Descriptive analyses (mean, median, min, max) of viral load assessed by the quantitative RT-PCR (RSV-A/B) of RSV-RTI, RSV-associated LRTI and severe LRTI cases will be tabulated. This analysis will also be done by study group.

The incidence rate of all-cause RTI (with 95% CI) will be calculated by group. The same descriptive analysis will be performed for all cause LRTI and all cause severe LRTI. These will also be presented for each viral etiology identified by multiplex PCR.

The incidence rate of asymptomatic RSV infections (with 95% CI) detected by the quantitative PCR (RSV-A/B) will be tabulated by group. Descriptive analyses (mean,

median, min, max) of viral load assessed by the quantitative RT-PCR (RSV-A/B) of those asymptomatic RSV infections will also be done by group.

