## 5. ANALYSIS SETS

### 5.1. Definition

#### 5.1.1. Total vaccinated cohort

The total vaccinated cohort (TVC) will include all subjects with at least one study vaccine administration documented.

- A safety analysis based on the TVC will include all vaccinated subjects.
- An immunogenicity analysis based on the TVC will include all vaccinated subjects for whom immunogenicity data are available.

The TVC analysis will be performed per treatment actually administered at Dose 1.

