### **5.2.1. Elimination from Exposed Set (ES)**

Code 1030 (Study vaccine not administered at all) and code 900 (invalid informed consent or fraud data) will be used for identifying subjects eliminated from ES

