### 6.3. Analysis of RSV incidence

The assessment of RSV analysis incidence and severity will be performed on the Exposed Set on RSV groups, placebo groups, pooled RSV and pooled Placebo groups separately for first RSV season (Day 1-366) and second RSV season (Days 367-731) and overall (Days 1-731).

The analysis will be performed according to all case definitions presented in [Table 5](#).

The proportion of subjects with at least one RSV infection and number of infections experienced by subjects meeting each of the case definition in [Table 5](#) (with 95 % CI) will be calculated by group.

The number of RSV infections within each group and the maximum disease severity of the event will be tabulated. The number of RSV infections within each group and frequency of hospitalization will be tabulated. The number of infections in each group and descriptive analysis of the viral load associated with the maximum disease severity of the event will be tabulated (mean, median, min, max). Descriptive analysis on maximum viral load per subject based on qRT-PCR confirmed RSV infection of maximum severity will be performed.

The viruses identified in the Respiratory Viral Panel will be tabulated to those events where RSV-RTI was identified to describe frequency of co-infections and responsible viruses. These tables will be repeated limited to RVP results of cases of confirmed LRTI and RSV-LRTI.

After looking at the frequency of coinfection of all confirmed LRTI and RSV-LRTI, if there will be more than 10% coinfections (RSV infection with identification of another viral pathogen on RVP), tables will be reproduced including those RSV episodes where co-infection was present and those where no other respiratory viral pathogen was identified. The descriptive analysis on viral load table will not be repeated on subject with at least one episode with maximum viral load.

Listing will be presented for all cases of RSV infection until Day 731 with the details of gender, age at episode, country, site, day of event (i.e days since first visit), classification according to maximum severity of episode as RSV RTI/RSV LRTI/ RSV severe LRTI and RSV very severe LRTI, RSV hospitalization 'Yes/No', SpO2 value, respiratory rate, result of RSV qRT-PCR and RVP result will be presented.

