RSV-Hd = High dose ChAd155-RSV vaccine (5 x 10^10 vp)

Placebo-Ld = Non-active control (0.5 ml)

Placebo-Md = Non-active control (0.15 ml)

Placebo-Hd = Non-active control (0.5 ml)

RSV = ChAd155-RSV vaccine (low/ middle/high dose pooled groups)

Placebo = Non-active control (0.5/0.15/0.5 ml pooled groups)

\* Association to RSV based on central testing only for asymptomatic visit (no local test available)

§Confirmed RSV infection and hospitalized for acute medical condition

N = number of subjects in each group

n\*\* = number of cases in each category

n/%= number/percentage of subjects reporting at least once the case

95%CI= Exact 95% confidence interval; LL = lower limit, UL = upper limit

Please note – Single episode can be considered in multiple category depending on the symptom experienced

**Template 44 Number and percentage of subjects reporting the RSV infection of different severity by number of events experienced between vaccination dose 1 up to D366/D731 visit <Exposed Set>**

		<Each group> N=xx			
				95% CI	
Characteristics	Categories	n	%	LL	UL
RSV infection-symptomatic or asymptomatic*	0				
	1				
	2				
RSV-RTI	0				
	1				
RSV-LRTI	0				
	1				
	2				
RSV-Severe LRTI	0				
	1				
RSV-very severe LRTI	0				
	1				
All cause LRTI	0				
	1				
	2				
	3				
RSV hospitalization§	0				
	1				
	2				
	3				

RSV-Ld = Low dose ChAd155-RSV vaccine ( $5 \times 10^9$  vp)

RSV-Md = Middle dose ChAd155-RSV vaccine ( $1.5 \times 10^{10}$  vp)

RSV-Hd = High dose ChAd155-RSV vaccine ( $5 \times 10^{10}$  vp)

Placebo-Ld = Non-active control (0.5 ml)

Placebo-Md = Non-active control (0.15 ml)

Placebo-Hd = Non-active control (0.5 ml)

RSV = ChAd155-RSV vaccine (low/ middle/high dose pooled groups)

Placebo = Non-active control (0.5/0.15/0.5 ml pooled groups)

N = number of subjects in each group

n = number of subjects in a given category

% =  $100 \times n/N$

LL, UL for percentage = Exact 95% Lower and Upper confidence limits

Please note – Single episode can be considered in multiple category depending on the symptom experienced

\* Association to RSV based on central testing only for asymptomatic visit (no local test available)

§Confirmed RSV infection and hospitalized for acute medical condition

**Template 45 Number and percentage of RSV infections and associated disease severity between vaccination dose 1 up to D366/D731 visit <Exposed Set>**

	Group N =				Total N =			
			95% CI				95% CI	
Categories	n	%	LL	UL	n	%	LL	UL

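### The RSV tables divide by every vaccinated infant and have no place for infants no longer followed, so the Days 367-731 percentages read low by the fraction lost

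*SAP*

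**What the plan says.** SAP 6.3 places the RSV analysis on the Exposed Set, by group and pooled, for a first season (Days 1-366), a second (Days 367-731) and overall (Days 1-731). The summary is "The proportion of subjects with at least one RSV infection and number of infections experienced by subjects", for each case definition in SAP Table 5.

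The Exposed Set is the renamed total vaccinated cohort: "The total vaccinated cohort (TVC) will include all subjects with at least one study vaccine administration documented" (SAP 5.1.1). Withdrawal does not remove anyone from it. SAP 5.2.1 names only two grounds: "Code 1030 (Study vaccine not administered at all) and code 900 (invalid informed consent or fraud data) will be used".

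In Templates 43 and 44 the footnote reads "N = number of subjects in each group", and Templates 53 and 54 carry the same definition. Template 43 defines the percentage as "n/%= number/percentage of subjects reporting at least once the case". Templates 43 and 53 have a No Infection row; Templates 44 and 54 have a 0 category. None has a row for infants not followed.

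Protocol 10.2.1 describes a withdrawn subject as one for whom "no follow-up has been performed and no further information has been collected for this subject from the date of withdrawal/last contact", while data up to that date stay in the analysis. Protocol 10.2 says withdrawals are not replaced.

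**The concern.** A percentage over all vaccinated infants treats each of them as observed for the whole period. Over two years of monthly or weekly contacts some families can be expected to leave, and Protocol Appendix D (rationale for Amendment 2) records that parents found the visits and blood tests demanding. An infant who leaves on Day 90 has no time at risk in Days 367-731, yet stays in that denominator and can only fall in No Infection or 0.

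The RSV sections give no rule that prevents this. Protocol 11.6.4 and 11.10 and SAP 6.3 and 11.3.6 define neither an at-risk denominator, nor time at risk, nor censoring. Other tables in the same SAP do condition on data: Templates 24 and 25 count subjects with available laboratory results, Template 37 counts subjects with available titres, and Template 42 shows the number missing.

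At stake is the second-year safety read-out on RSV disease. Protocol Appendix D records that this year of follow-up was added at a national authority's request, and Protocol 1.2.2.1 says the study informs a later trial in seronegative infants.

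**Working it through.** The plan states no RSV attack rate, dropout rate or expected case count, so there is no figure of its own to reproduce. Group sizes come from the Protocol: up to 48 vaccine and 48 placebo recipients (Synopsis), with 32 to 48 on vaccine (Section 1.3). The risk per period p and the fraction lost d are assumptions, and loss is taken as unrelated to RSV risk.

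**Step 1. Days 367-731.** Of N infants, a fraction d has left before Day 367. Cases arise only among the N(1 - d) still followed, so the reported percentage is N(1 - d)p / N = p(1 - d).

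| True risk p | d = 5% | d = 10% | d = 20% | d = 30% |
|---|---|---|---|---|
| 5% | 4.8% | 4.5% | 4.0% | 3.5% |
| 10% | 9.5% | 9.0% | 8.0% | 7.0% |
| 20% | 19.0% | 18.0% | 16.0% | 14.0% |
| 30% | 28.5% | 27.0% | 24.0% | 21.0% |

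The relative shortfall is exactly d.

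**Step 2. Days 1-731.** With the same p in each period, the true two-year risk is 1 - (1 - p)². An infant infected before leaving still counts, so the reported value is p + (1 - p)(1 - d)p.

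- p = 10%: true 19.0%. At d = 10% it reads 0.10 + 0.90 × 0.90 × 0.10 = 18.1%; at d = 20%, 17.2%.
- p = 20%: true 36.0%. At d = 10% it reads 34.4%; at d = 20%, 32.8%.

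At 20% loss the relative shortfall is about 9% (1.8/19.0 and 3.2/36.0), under half that of Step 1. Spreading exits evenly over two years changes these results by at most 0.4 points for p of 5-30% and d of 5-30%.

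**Step 3. Intervals.** Take 5 infected infants in Days 367-731 in a pooled arm of 48 (exact 95% CIs).

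- Planned denominator: 5/48 = 10.4% (3.5 to 22.7), width 19.2 points.
- If 5 had left: 5/43 = 11.6% (3.9 to 25.1), width 21.2 points.
- If 10 had left: 5/38 = 13.2% (4.4 to 28.1), width 23.7 points.

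**Step 4. Between arms, Days 367-731.** The reported ratio is the true ratio × (1 - d_v)/(1 - d_p), for vaccine loss d_v and placebo loss d_p. Equal loss leaves the ratio unchanged. With d_p = 5%:

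- A true ratio of 1.5 reads 1.42, 1.26 and 1.11 at d_v = 10%, 20% and 30%.
- A true ratio of 2.0 reads 1.89, 1.68 and 1.47.
- The ratio reads 1.0 only when d_v = 1 - (1 - d_p)/ratio: 24% for a true ratio of 1.25, 37% for 1.5 and 53% for 2.0.

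**The case against.** The strongest reply is that the SAP follows the protocol. Protocol 11.10 plans proportions on the total vaccinated cohort for RSV-RTI, RSV-LRTI and severe LRTI. This stands.

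A reader might infer more: that the protocol required person-time and the SAP dropped it without listing the change in its Section 9. The documents do not support that. Protocol 11.10 uses the term only for all-cause RTI and LRTI and for asymptomatic infection ("The incidence rate of asymptomatic RSV infections (with 95% CI"), and defines no time at risk. Protocol 9.10.5 and 11.4 use the same term for a plain proportion of subjects.

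Second, no text says leavers are to be classed as uninfected. That is correct: it follows from the rows combined with the denominator. The template titles run from Dose 1 to D366 or D731, so no shell is specific to Days 367-731, and SAP Annex 3 calls the displays illustrative. But SAP 6.3 and SAP Table 3 both require the Days 367-731 analysis, and nothing gives it another denominator.

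Third, Protocol 11.6.2 and SAP 11.3.5 openly count no report as no event for unsolicited AEs and SAEs, and Protocol Section 4 calls the RSV case definitions part of a safety analysis. That makes the convention familiar, but neither section states it for the RSV tables.

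Fourth, attrition is visible by group in Templates 2 and 3, and short follow-up is reported by group (SAP 5.3). A reader can see the loss. The summary tables alone do not give the percentage among those followed for each category and period.

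Fifth, SAP 6.4.1.2 plans no vaccine-placebo contrast for RSV outcomes, SAP Section 7 calls all analyses descriptive, and parents stay blinded to Day 730. The documents therefore give no reason to expect strongly unequal dropout.

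**Conclusion.** The point holds as a weakness of the measure. If any infant leaves before Day 367, the Days 367-731 percentages fall below the risk among infants still followed, by the fraction lost in relative terms. The two-year percentages are lowered less.

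The size depends on dropout, which the documents do not give. At 5-10% loss the shift is 1 point or less for risks up to 10%, and up to 3 points for a 30% risk. That is small beside an exact interval about 19 points wide for 5/48. At 20% loss a 20% risk reads 16%. The intervals are also somewhat too narrow, because unobserved infants count as observed non-events.

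It is tempting to conclude that the tables could conceal an excess of RSV disease on vaccine. Partial dilution is possible if more vaccine than placebo infants leave. Full concealment of a ratio of 1.5 or more would need 37% or more vaccine loss against 5% on placebo, and nothing in the documents suggests that.

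The denominator itself is certain from the text. The classification of leavers is inferred from the table layout, and the sizes assume that loss is unrelated to RSV risk.

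**What to change.** Keep the planned Exposed Set proportions. Replacing that denominator outright would select on retention after randomization, and an infant leaving on Day 370 would still count as fully observed. In SAP 6.3 and Templates 43, 44, 53 and 54, add for each period and group:

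- the number of infants under surveillance at the start of the period, and the percentage on that denominator;
- the rate per infant-year with 95% CI, with time at risk from Dose 1 (or Day 367) to the last recorded surveillance contact or visit, stating whether first cases or all episodes are counted;
- a split of No Infection (or 0) into followed to the end of the period and not followed to the end of the period.

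The data are already collected: "Contacts for active and passive surveillance will be recorded in the eCRF" (Protocol 6.6.14), and SAP 13.1 already lists surveillance contacts as an individual data listing. The cost is SAP wording, extra table columns and slightly wider intervals on the added measures.

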**Table 5 Case definition of RSV- RTI/LRTI**

RSV infection	Symptomatic and/or asymptomatic RSV infection
RSV-RTI	Runny nose OR blocked nose OR cough AND Confirmed RSV infection 
RSV-LRTI	History of cough OR difficulty breathing  AND SpO 2 < 95%  , OR RR increase  AND Confirmed RSV infection 
RSV-severe LRTI	Meeting the case definition of RSV-LRTI AND SpO 2 < 93%  , OR lower chest wall in-drawing
RSV-very severe LRTI	Meeting the case definition of RSV-LRTI AND SpO 2 < 90%  , OR inability to feed, OR failure to respond / unconscious
RSV hospitalization	Confirmed RSV infection  AND Hospitalized for acute medical condition 
All-cause LRTI	History of cough OR difficulty breathing  AND SpO 2 < 95%  , OR RR increase 

Definition based on [Modjarrad, 2016]

LRTI = lower respiratory tract infections; RR = respiratory rate; RTI = respiratory tract infections;

SpO2 = blood oxygen saturatin

 Based on history reported by parents/LARs and includes difficulty breathing (e.g. showing signs of wheezing or stridor, tachypnoea, flaring [of nostrils], chest in-drawing, apnoea) associated with nasal obstruction

 For blood oxygen saturation (SpO2), the lowest value monitored will be used

 RR increase defined as ≥ 40/minute (12 months of age or above)

 RSV infection confirmed on nasal swab positive for RSV A or B by quantitative Reverse Transcription Polymerase Chain Reaction (qRT-PCR)

 RSV sampling and testing is based on medical judgment of medical practitioner or driven by algorithm

 Hospitalization is defined as a medical decision that the infant requires admission for observation or treatment

- For the analysis of RSV-RTI episode, the start date of an RTI episode will be defined as the first day of any occurrence of cough, runny nose, blocked nose, and a new case requires an interval of at least 7 symptom free days since the last episode of RTI that was diagnosed.
- For the analysis of RSV-LRTI or severe or very severe LRTI the start date of the LRTI episode is defined as the point at which the first symptoms of cough, or difficulty breathing were observed and a new case requires an interval of at least 7 symptom free days since the last episode of LRTI that was diagnosed.

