RSV asymptomatic (Excluding RSV-RTI, LRTI, RSV-severe LRTI or RSV-very severe LRTI)								
RSV RTI (Excluding LRTI, RSV-severe or very severe LRTI)								
RSV LRTI (Excluding RSV-severe or very severe LRTI)								
RSV-severe LRTI (Excluding RSV-very severe LRTI)								
RSV-very severe LRTI								

RSV-Ld = Low dose ChAd155-RSV vaccine (5 x 10^9 vp)

RSV-Md = Middle dose ChAd155-RSV vaccine (1.5 x 10^10 vp)

RSV-Hd = High dose ChAd155-RSV vaccine (5 x 10^10 vp)

Placebo-Ld = Non-active control (0.5 ml)

Placebo-Md = Non-active control (0.15 ml)

Placebo-Hd = Non-active control (0.5 ml)

RSV = ChAd155-RSV vaccine (low/ middle/high dose pooled groups)

Placebo = Non-active control (0.5/0.15/0.5 ml pooled groups)

\* Association to RSV based on central testing only for asymptomatic visit (no local test available)

N = number of RSV positive samples in each group

n\*\* = number of cases in each category

n/% = number/percentage of cases in each category

95%CI= Exact 95% confidence interval; LL = lower limit, UL = upper limit

Please note – Single episode is considered in single category of highest severity based on the symptom experienced

**Template 46 Number and percentage of RSV infections requiring hospitalization  
 between vaccination dose 1 up to D366/D731 <Exposed Set>**

	Group N =					Total N =				
	n**	n	%	95% CI		n**	N	%	95% CI	
Categories	n**	n	%	LL	UL	n**	N	%	LL	UL
RSV RTI*(Excluding LRTI, severe or very severe LRTI)										
RSV LRTI (Excluding severe or very severe LRTI)										
RSV-severe LRTI (Excluding very severe LRTI)										
RSV-very severe LRTI										

RSV-Ld = Low dose ChAd155-RSV vaccine (5 x 10^9 vp)  
 RSV-Md = Middle dose ChAd155-RSV vaccine (1.5 x 10^10 vp)  
 RSV-Hd = High dose ChAd155-RSV vaccine (5 x 10^10 vp)  
 Placebo-Ld = Non-active control (0.5 ml)  
 Placebo-Md = Non-active control (0.15 ml)  
 Placebo-Hd = Non-active control (0.5 ml)  
 RSV = ChAd155-RSV vaccine (low/ middle/high dose pooled groups)  
 Placebo = Non-active control (0.5/0.15/0.5 ml pooled groups)  
 N = number of RSV infections in each group  
 n\*\* = number of cases in each category  
 n/%= number/percentage of subjects reporting at least once the case  
 95%CI= Exact 95% confidence interval; LL = lower limit, UL = upper limit

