**Template 47 Descriptive statistics of viral load calculated on all qRT-PCR confirmed RSV infection episodes with varying disease severity from vaccination dose 1 up to D366/D731 <Exposed Set>**

Symptoms	Parameters	Group N=		
		Value	LL	UL
RSV asymptomatic* (Excluding RSV-RTI, RSV-LRTI, RSV-severe LRTI or RSV-very severe LRTI)	n			
	GM			
	95% CI			
	SD			
	Q1			
	Median			
	Q3			
	Min/Max			
RSV RTI (Excluding RSV-LRTI, RSV-severe LRTI or RSV-very severe LRTI)				
RSV LRTI (Excluding RSV-severe or RSV-very severe LRTI)				
RSV-severe LRTI (Excluding RSV-very severe LRTI)				
RSV-very severe LRTI				
RSV hospitalization§				

RSV-Ld = Low dose ChAd155-RSV vaccine (5 x 10^9 vp)  
 RSV-Md = Middle dose ChAd155-RSV vaccine (1.5 x 10^10 vp)  
 RSV-Hd = High dose ChAd155-RSV vaccine (5 x 10^10 vp)  
 Placebo-Ld = Non-active control (0.5 ml)  
 Placebo-Md = Non-active control (0.15 ml)  
 Placebo-Hd = Non-active control (0.5 ml)  
 RSV = ChAd155-RSV vaccine (low/ middle/high dose pooled groups)  
 Placebo = Non-active control (0.5/0.15/0.5 ml pooled groups)  
 N = number of RSV infections episodes in each group  
 n= Number of events in each category  
 SD=Standard Deviation  
 Q1 and Q3 = 1st and 3rd quantiles  
 Min/Max = Minimum/Maximum  
 GM = Geometric mean

LL, UL for GM = Exact 95% Lower and Upper confidence limits  
 Total RSV viral load computed as RSV A Viral load + RSV B Viral load

\* Association to RSV based on central testing only for asymptomatic visit (no local test available)

§Confirmed RSV infection and hospitalized for acute medical condition

Please note: each episode for a subject is considered to be independent. We may have multiple swab for one episode. We have considered the swab with maximum viral load from one episode for the table

Please note – Except for RSV hospitalization, single episode is considered in single category of highest severity based on the symptom experienced

Please check:- To check for cases where asymptomatic swab has been taken but the subject hasve symptoms of RTI or LRTI. In this case, asymptomatic is also considered as RSV RTI/LRTI and maximum viral load of all the episode should be considered.

**Template 48 Descriptive statistics of maximum viral load per subjects based on qRT-PCR confirmed episode with varying disease severity form vaccination dose 1 up to D366/D731 <Exposed Set>**

	Parameters	Each Group		
		N=	95% CI	
Symptoms	Value	LL	UL	

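### SAP Templates 45 and 46 mix counting units: severity is given as episodes over RSV-positive samples, and hospitalisation as subjects over infections

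*SAP*

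**What the plan says.** SAP section 6.3 plans two infection-level summaries: infections per group by the worst severity reached, and infections per group with how often they led to admission. Templates 45 and 46 in SAP section 13.2 are the mock tables for these.

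- **Template 45.** The title is "Number and percentage of RSV infections and associated disease severity". Five rows run from asymptomatic to very severe LRTI, each leaving out the more severe ones. The allocation rule is "Single episode is considered in single category of highest severity based on the symptom experienced", the numerator is "n/% = number/percentage of cases in each category", and the denominator is "N = number of RSV positive samples in each group".
- **Template 46.** The title is "Number and percentage of RSV infections requiring hospitalization". N is the number of RSV infections in the group, but the percentage is defined by "n/%= number/percentage of subjects reporting at least once the case". A separate column, n**, gives cases.
- **Template 47** (viral load). N is infection episodes. Its note says "We may have multiple swab for one episode" and keeps only the swab with the highest load, for that table.
- **SAP section 11.3.6.** For symptomatic RTI, "a new case requires an interval of at least 7 symptom free days since the last episode of RTI that was diagnosed". Table 5 in the same section counts asymptomatic infection as RSV infection, but gives no matching rule for a positive swab without symptoms.

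**The concern.** Template 45 asks how severe an infection is once it has occurred. Its numerator counts episodes and its denominator counts swabs. The number of positive swabs per episode depends on how long a child sheds virus and how often the child is sampled. Neither is a measure of severity, and either could differ between vaccine and placebo.

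Several positives per episode are plausible under the protocol. Swabs are taken monthly in the RSV season (Protocol 9.2.2) and from every child with RTI symptoms at an assessment visit (9.2.4). Worsening may prompt a repeat visit (9.2.4), and a further sample is optional if the previous specimen was RSV-positive (Figure 3, note 6).

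In Template 46 the numerator and denominator are again different things, children and infections. In both tables the planned exact interval (Clopper-Pearson, SAP 11.2) assumes that the counted units are a subset of N, and here they are not.

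**Working it through.** The documents state no figure on this point, so there is none to reproduce. The definitions come from the template notes. The counts below are assumptions for illustration.

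**Template 45.** Let E be the infection episodes in an arm, x those whose highest severity is the category of interest, and k the mean positive samples per episode.

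- Share on the infection unit: x / E.
- Share as the note is written: x / (E × k) = (x / E) / k.
- Total of the five exclusive categories as written: E / (E × k) = 1 / k.

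Assume E = 20 and x = 4 LRTI, so the infection-level share is 4/20 = 20.0%, and let k run from 1 to 2:

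| k | N (samples) | LRTI share as written | Exact 95% CI | Categories total |
|---|---|---|---|---|
| 1.0 | 20 | 4/20 = 20.0% | 5.7 to 43.7 | 100% |
| 1.25 | 25 | 4/25 = 16.0% | 4.5 to 36.1 | 80% |
| 1.5 | 30 | 4/30 = 13.3% | 3.8 to 30.7 | 66.7% |
| 2.0 | 40 | 4/40 = 10.0% | 2.8 to 23.7 | 50% |

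The interval is also too narrow. At k = 2.0 it spans 23.7 − 2.8 = 20.9 points, against 43.7 − 5.7 = 38.0 points on the 20 infections actually observed.

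If two arms have the same true severity, the ratio of their printed shares is the inverse ratio of their k values. With k = 1.0 in one arm and 2.0 in the other, the table shows 20.0% against 10.0% with no real difference. The arm with fewer positive swabs per episode looks more severe.

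**Template 46.** Assume 20 infections in 16 children, with 3 hospitalised infections in 2 children, the repeat admission falling in the same severity category.

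- As written, subjects over infections: 2/20 = 10.0% (1.2 to 31.7).
- Infections over infections: 3/20 = 15.0% (3.2 to 37.9).
- Subjects over infected subjects: 2/16 = 12.5% (1.6 to 38.3).

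If no child is hospitalised twice in one category, the count of children equals the count of cases, and the printed percentage equals the infection-level one.

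**Symptom-free repeat positives.** Suppose Template 45's N is changed to episodes but later symptom-free positives count as new infections. With 5 extra, the LRTI share becomes 4/25 = 16.0%; with 10 extra, 4/30 = 13.3%. Changing N therefore does not fully settle the denominator until the SAP says when such a swab is a new infection.

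**The case against.** The best defence is that these are errors in mock-table notes and not a chosen analysis. Section 6.3 already has the right unit. SAP section 13 says that the displays and footnotes are examples to be tailored, and that minor changes need no amendment. The notes look carried over: Template 45 defines an n** column that it does not have, and Template 46's n/% line repeats Template 43's, where N really is subjects. The Template 45 error would probably be noticed, since the counts are printed and exclusive categories would not reach 100%. All analyses are descriptive (SAP section 7).

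Much of this stands, and it limits the weight of the point. It does not remove it. SAP section 10 refers to the study-specific mock tables for layout, the denominators are defined nowhere else, and permission to adapt a footnote does not ensure that it is corrected. A rule for linking swabs into infections is a derivation, not an editorial matter.

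A reader might infer two stronger things that the documents do not support.

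- **That the search for enhanced RSV disease rests on these tables.** Protocol 1.2.4.4 relies on LRTI and severe LRTI incidence by group. Protocol 11.10 plans proportions of subjects, and the IDMC receives incidence reports (Protocol 9.10.3). Templates 43, 44 and 53 use subjects as N, and cases are also listed individually.
- **That the SAP never merges repeat swabs.** Template 47 keeps one swab per episode and folds a routine swab taken during symptoms into the symptomatic episode. Template 48 is per subject, and symptomatic episodes have the 7-day rule. The gap is confined to Template 45's N and to positives without symptoms.

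**Conclusion.** The point holds in a limited form. As written, Template 45's percentages and exact intervals are wrong whenever any episode has more than one positive sample, and the understatement factor is exactly the mean number of positive samples per episode. Going from 20% to 10% rests on assumed counts and on two positive swabs per episode. The documents give no swab ratio, so no particular excess in either arm can be claimed.

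Template 46 is a minor inconsistency. Its percentage and interval are off only if a child is hospitalised for more than one infection in the same category, and n** over N already gives the infection-level ratio.

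The subject-level percentages in Templates 43, 44 and 53 are free of the unit mismatch, so the main incidence results stand. Counts of infections per subject, as in Templates 44 and 54, still depend on the missing rule for symptom-free repeat positives; that is a secondary point.

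**What to change.** 1. In Template 45, set N to the number of RSV infection episodes in the group, as in Template 47. The categories then total 100% whatever the number of swabs.
2. In Template 46, use one unit for n, the percentage and the interval: hospitalised infections over infections (n** over N), or hospitalised subjects over infected subjects. The first matches the title and section 6.3.
3. As a secondary change, state in SAP 11.3.6 when a symptom-free positive swab after an earlier positive belongs to the same infection. Keep the 7-symptom-free-day rule for symptomatic episodes, and do not merge across RSV seasons or across RSV-A and RSV-B. Simply joining all consecutive positives would break those limits, because routine swabs stop outside the season.

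The cost is two corrected notes, one added rule and an episode identifier, which Template 47 already needs. Any linking rule will misclassify an occasional true re-infection. Episode-based intervals still treat several episodes in one child as independent, as the Template 47 note already does. The changes should be in place before the Day 366 analysis, when SAP Table 3 first schedules the RSV tables.
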